4 ANALYSIS SETS/POPULATIONS

Analysis population will be all patients identified from the Syapse Learning Health Network database who meet the following inclusion and exclusion criteria-

Inclusion criteria

Patients must meet all of the following inclusion criteria to be eligible for inclusion in the study:

1. *Female or male sex.*
2. *Diagnosis (confirmed by clinical review) of A/MBC, defined as breast cancer at stage IIIB, stage IIIC, stage IV or identified as having distant metastasis.*
3. *Age ≥ 18 years at A/MBC diagnosis.*
4. *Initiated palbociclib in combination with an AI as first-line therapy after A/MBC diagnosis on or after 03 February 2015 through 31 July 2019. Note that the date of the start of the inclusion period reflects the month of palbociclib US FDA approval.*
5. *Evidence of ER or PR positive disease, or absence of any indication of ER and PR negative disease closest to A/MBC diagnosis (ie patients are eligible without affirmative indication of ER/PR+ status as long as ER/PR- indication is not present).*
6. *Evidence of HER2 negative disease, or absence of any indication of HER2 positive disease closest to A/MBC diagnosis (ie patients are eligible without affirmative indication of HER2- status as long as HER2+ indication is not present).*

Exclusion criteria

Patients meeting any of the following criteria will not be included in the study:

[figure not shown]
[figure not shown]
1. *Enrollment in an interventional clinical trial for A/MBC during the study observation period.*
2. *Evidence of prior treatment with any CDK4/6 inhibitor in the adjuvant setting (i.e. a CDK4/6 inhibitor is administered (start date) > 30 days prior to the A/MBC diagnosis date).*
3. *Evidence of another primary cancer within 3 years prior to the initial line containing palbociclib.*

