9.2 APPENDIX 2: Description of data elements used in the study

The following data elements will be extracted from feeds and/or curated by Certified Tumor Registrars (CTRs) for this study:

Data Elements	Description
Demographic characteristics	
Date of birth	Year, month, day (Availability of the exact date will depend on the Expert de-ID approach)
Date of initial BC diagnosis	Date of initial breast cancer (BC) diagnosis
Date of A/MBC diagnosis	Date of advanced/metastatic breast cancer (A/MBC) diagnosis
Patient sex	Male, Female, Transsexual, Other, Not Provided
Primary race	American Indian/Alaska Native; Asian; Black/African American/Native Hawaiian/Pacific Islander; White; Not Provided; Other (Exact list will depend on the expert de-ID approach)
Secondary race	(if provided) (Exact list will depend on the expert de-ID approach)
Ethnicity	Non-Hispanic/Non-Latino; Hispanic/Latino; Unknown (Exact list will depend on the expert de-ID approach)
Region of residence	Northeast, Midwest, South, West Captured at A/MBC diagnosis (Exact list will depend on the expert de-ID approach)
Insurance type	Medicare/Medicaid; Commercial; Commercial and Medicare/Medicaid; None; Not Provided Captured at 1) date of A/MBC diagnosis; and 2) at initiation of palbo
Menopause status	Premenopausal; Postmenopausal; Perimenopausal; Unknown; Not applicable. Captured on date closest to but before: 1) A/MBC diagnosis; and 2) initiation of palbo

PFIZER CONFIDENTIAL

	
Menopausal status: captured if explicitly stated in clinician notes. Otherwise captured based on following definition of menopause from NCCN Guideline v.3.2019:
 
Prior bilateral oophorectomy (date of surgery)
 
Age >=60 years old
 
Age <60 years old and amenorrheic for 12 months+ in the absence of chemotherapy, tamoxifen, toremifene, or ovarian suppression.
 
Additionally, type, name, and start/end date of ovarian suppression agent is captured

Date of death	If patient vital status = deceased, date of death from the medical record (capturing from EMR, registries, third party integrations) (Availability of the exact date will depend on the Expert de-ID approach)
Last contact date	If patient is alive (not deceased), date of the last contact by a healthcare provider from the medical record (Availability of the exact date will depend on the Expert de-ID approach)
Clinical characteristics	

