Breast cancer histology	List captured at initial breast cancer diagnosis including: Adenoid cystic; Cribriform; Ductal; Inflammatory; Intraductal; Lobular; Medullary with lymphoid stroma; Medullary, NOS; Mucinous; Paget's disease and infiltrating; Paget's disease and intraductal; Papillary; Secretory; Squamous cell; Tubular, and more
ECOG/KPS performance score	Score captured on date closest to (with a ± 60 day cutoff around) 1) A/MBC diagnosis; and 2) initiation of palbo
Stage at initial BC diagnosis	0, I, IA, IB, II, IIA, IIB, III, IIIA, IIIB, IIIC, IV, Unable to stage, Not found, Not applicable
Presence of distant metastasis	
Yes; No
 
Note: this variable would be "yes" if patient is diagnosed with de novo metastatic breast cancer or if patient developed metastasis after initial breast cancer diagnosis

Date of first distant metastasis	Same as initial BC diagnosis if de novo metastatic BC, otherwise captured as date that the patient developed distant metastatic disease
Site(s) of distant metastasis at MBC diagnosis	
Bone; Chest Wall; Contralateral Breast; Distant Lymph node(s); Liver; Lung; Peritoneum; Pleural nodules; Malignant pleural effusion; Skin; Brain (brain and spinal metastases); Ovary; Undocumented; Other, Specify;
 
Visceral sites (Liver, Lung, Peritoneum and Pleural nodules);

PFIZER CONFIDENTIAL

	Bone only
Comorbidities	List of comorbidities at time of A/MBC diagnosis (sourced from problem list encompassing entire patient journey and confirmed from clinician notes), including: anemia, heart arrhythmia, hypertension, myocardial infarction, congestive heart failure, peripheral vascular disease, cerebrovascular accident, hemiplegia, chronic obstructive pulmonary disease, ulcer disease, diabetes with chronic complications, diabetes without chronic complications, renal disease, connective tissue disease such as rheumatoid arthritis or lupus, Alzheimer's or other dementia, cirrhosis or other serious liver disease, non-breast cancer malignancy (excluding sites of breast cancer metastasis and malignant neoplasm of skin), metastatic solid tumor (other than breast cancer), HIV/AIDS, and other comorbidities of interest
Note: comorbidities in bold are in CCI; CCI listed in derived variables section	
Biomarkers	
ER, PR, HER2 status	Positive; Negative; Equivocal; Unknown

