ER, PR, HER2 test type	ISH, IHC, NGS, PCR, Other, Unknown
ER, PR, HER2 sample collection date	Year, month, day
ER, PR, HER2 report date	Year, month, day
BRCA status	BRCA1 Mutation; BRCA2 Mutation; BRCA NOS Mutation
BRCA sample collection date	Year, month, day
BRCA report date	Year, month, day
Treatment modalities prior to A/MBC diagnosis	
Breast surgery	Yes; No
Surgery type	Partial mastectomy; Lumpectomy / excisional biopsy; Segmental mastectomy; Subcutaneous mastectomy; Total mastectomy; Modified radical mastectomy; Radical mastectomy; Extended radical mastectomy; Mastectomy, NOS; Surgery, NOS
Note: if multiple, all will be listed (longitudinal data)	

PFIZER CONFIDENTIAL

Surgery date	Year, month, day
Breast radiation therapy	Yes; No
Radiation therapy site	Whole breast; Partial breast; Chest wall; Regional lymph nodes; Unknown Note: limited to primary breast cancer site. If multiple, all will be listed (longitudinal data)
Radiation start/end dates	Year, month, day
Chemotherapy	Yes; No
Recurrence	
Patient had recurrence	Yes; No
Recurrence date	Year, month, day (Captures first time locally, first time regionally, and first time distant; if multiple sites, hierarchy prioritizes most advanced site)
Recurrence site	Local; Regional; Distant; Unknown
Recurrence test source	Biopsy; Imaging; Imaging confirmed by biopsy; Unknown
Clinician confirmation of recurrence	Sources including: Medical oncology consult/note; Radiation oncology note; Discharge summary; Other
Recurrence linked to therapy	Yes; No
Progression	
Patient had progression	Yes; No
Progression date	Year, month, day
Progression test source	Biopsy; Imaging; Imaging confirmed by biopsy; Unknown
Clinician confirmation of progression	Sources including: Medical oncology consult/note; Radiation oncology note; Discharge summary; Other
Clinician confirmation date	Year, month, day

[figure not shown]
PFIZER CONFIDENTIAL

Progression linked to therapy	Yes; No
Complete systemic therapy history	
Therapy name	Therapy name
Administration route	Categories including: Oral; Infusion; Injection; Other; Unknown

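### Criteria 5 and 6 put no direction or time limit on the receptor result nearest A/MBC diagnosis, so a specimen taken after palbociclib + AI starts can decide eligibility

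*SAP*

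**What the plan says.** Section 4, inclusion criterion 6 requires either evidence that the disease is HER2-negative or "absence of any indication of HER2 positive disease closest to A/MBC diagnosis". Criterion 5 requires "Evidence of ER or PR positive disease, or absence of any indication of ER and PR negative disease closest to A/MBC diagnosis". Each is an either/or rule: affirmative evidence of the right receptor status, or no contrary indication. The explanatory note to criterion 6 adds that "patients are eligible without affirmative indication of HER2- status as long as HER2+ indication is not present", and criterion 5 has a matching note. Neither note carries a date limit.

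Appendix 2 (Section 9.2) does limit other baseline variables in time:
- Menopausal status: "Captured on date closest to but before: 1) A/MBC diagnosis; and 2) initiation of palbo".
- ECOG/KPS: "Score captured on date closest to (with a ± 60 day cutoff around) 1) A/MBC diagnosis; and 2) initiation of palbo".

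For receptors, the same appendix lists status, test type, report date and "ER, PR, HER2 sample collection date". It gives no rule for choosing among several results. Table 15.1.11 summarises specimen and report dates by calendar year only.

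**The concern.** All the effectiveness outcomes start at first-line therapy (Section 7.2), so cohort membership should be settled by what was known at that point. A nearest-result rule with no limit at treatment start lets later information into the cohort definition.

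Later tissue is foreseeable in these data. Appendix 2 allows progression to be identified from pathology and lists biopsy among the progression test sources. A specimen taken on treatment therefore exists mainly because the disease was thought to have progressed. If its result is adverse (HER2-positive, or ER and PR both negative) and it decides eligibility, the patient who leaves the cohort is usually an rwPFS event, and often an rwTTD and rwTTNT event too. The study has a single arm, so no comparator would absorb the distortion. The planned tables would not show it, because calendar years cannot be related to each patient's treatment start.

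**Working it through.** **Step 1. Can a post-treatment specimen be the nearest one?** Suppose the last earlier test lies X months before A/MBC diagnosis and a biopsy is taken Y months after it. The later specimen is nearer when Y < X. From Section 2.1, treatment starts between 03 February 2015 and 31 July 2019, and the assumed data cutoff is 01 February 2020. Potential follow-up therefore runs from 185 days (185/30.4375 = 6.1 months, matching the plan's stated 6-month minimum) to 1,824 days (59.9 months). Section 5.1 has a time-to-metastasis category above 36 months. A biopsy at Y = 12 is nearer than a primary-tumour test at X > 36, provided nothing was tested around A/MBC diagnosis. If something was, its distance is close to zero and a later specimen cannot be nearest.

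**Step 2. Who is affected under each reading of the either/or rule?**

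| Patient | Timing phrase governs both halves | Timing phrase governs second half only |
|---|---|---|
| Tested around A/MBC diagnosis | Unaffected | Cannot be removed; if that test was adverse, a later qualifying result could admit |
| Only an old qualifying result; later, nearer specimen adverse | Removed | Stays in through the first half |
| No earlier result; later specimen adverse | Removed (kept as unknown if never biopsied) | Removed (kept as unknown if never biopsied) |
| Only an old adverse result; later, nearer specimen qualifying | Admitted | Admitted through the first half |

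The third and fourth rows behave alike under both readings, so post-treatment information can decide eligibility whichever is meant. The readings differ on the second row, which is where recurrent patients with only an old primary-tumour result fall.

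**Step 3. Illustrative size for rwPFS.** The SAP gives no median, re-biopsy rate or receptor-change rate, so these inputs are assumptions: exponential rwPFS with median 20 months (λ = ln 2/20 = 0.03466), censoring uniform on 6 to 60 months, and a random fraction f of observed events removed. A patient still at risk at time t goes on to an observed event with probability

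p(t) = 1 − [exp(−λa) − exp(−λb)] / [λ(b − a)], where a = max(6 − t, 0) and b = 60 − t.

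This gives p(0) = 0.633, p(6) = 0.548 and p(20) = 0.459. Removing the fraction f multiplies the hazard at t by

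r(t) = (1 − f) / (1 − f·p(t)).

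For f = 0.05:
- r(0) = 0.95/(1 − 0.05 × 0.633) = 0.981
- r(6) = 0.95/(1 − 0.05 × 0.548) = 0.977
- r(20) = 0.95/(1 − 0.05 × 0.459) = 0.972

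Integrating λ·r(t) until it reaches ln 2 gives the new median. Patient counts use N = 350, the middle of the 300 to 400 expected in Section 2.1.

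| f | Share of cohort (f × 0.633) | Patients of 350 | Median, months | 24-month rwPFS |
|---|---|---|---|---|
| 0 | 0 | 0 | 20.0 | 43.5% |
| 2% | 1.3% | 4 | 20.2 | 43.9% |
| 5% | 3.2% | 11 | 20.5 | 44.4% |
| 8% | 5.1% | 18 | 20.8 | 45.0% |

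A simulation of 400,000 patients with the same inputs gave medians of 20.18, 20.49 and 20.80 for the three removal rates. Varying the assumed median from 15 to 25 months and f from 1% to 10% gives shifts from about 0.06 to about 1.6 months.

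**Step 4. Against sampling error.** With 350 × 0.633 ≈ 222 events, an exponential 95% interval around 20 months is 20 × exp(±1.96/√222) = 17.5 to 22.8. The Kaplan-Meier interval would be wider. Shifts of 0.2 to 0.8 months sit well inside it. These figures model removals only.

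**The case against.** The strongest reply is grammatical. The timing phrase sits in the second half of each criterion, and the explanatory notes speak only of patients without affirmative evidence. Affirmative evidence may therefore suffice on its own. A patient who was HR+/HER2- on an old primary tumour would then stay in whatever a later biopsy showed. That reading is plausible, and it narrows the problem to patients with no earlier qualifying result. It does not remove it, as the third and fourth rows of the table show.

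Second, the plan nowhere says that tests on either side of diagnosis count, or that progression biopsies are used. Section 2.1 and the title of Table 15.1.2 treat receptor status as a feature of the A/MBC diagnosis, which favours a baseline reading. This is fair: the point rests on a missing limit, not on a stated rule. But those passages set no cutoff either, and the plan sets one where it wants one.

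Third, the bias need not run one way. A late qualifying result can admit a patient who progressed, which shortens rwPFS. Tables 15.1.13 and 15.1.14 also provide for breast surgery after metastasis, so a later specimen need not mean progression. Both points stand and soften the claim about direction.

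Fourth, the effect is small, the removal rates are assumed, and Section 3 has no decision rule for it to upset. This stands too, and it limits the priority of the point. It does not justify leaving the clause open, since the remedy is a date filter.

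Finally, Section 2 says italicised text comes from the protocol, and the criteria are italicised. Test-selection detail may be in that document, which is not at hand. If it is, the SAP should repeat it.

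**Conclusion.** The point holds in limited form. As written, criteria 5 and 6 allow a specimen collected after palbociclib + AI start to decide eligibility, while menopausal status and ECOG/KPS have time limits. If the timing phrase governs both halves of each rule, those exposed are mainly recurrent patients with only an old primary-tumour result. If it governs the second half alone, they are only patients with no earlier qualifying result.

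The net effect on rwPFS, rwTTD and rwTTNT is probably favourable but not certainly so. Its likely size is about 0.2 to 0.8 months on a 20-month median rwPFS. That assumes exponential times, uniform censoring, random removal of 2% to 8% of observed events and no offsetting admissions; none of these inputs comes from the SAP. Only rwPFS was calculated. The effect on rwOS was not computed, and no size is claimed for it.

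A reader might infer more: that the plan deliberately uses progression biopsies, that any patient with an old HR+/HER2- result would be dropped after an adverse re-biopsy, or that patients who do not progress can never be removed. The documents support none of these. The first is read into silence, the second depends on one of two possible readings, and the third overlooks specimens from later surgery.

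**What to change.** In criteria 5 and 6, and for Table 15.1.10, use only ER/PR and HER2 results from specimens collected on or before the palbociclib start date, and among those take the one closest to A/MBC diagnosis. Treat patients with no such specimen as unknown, who remain eligible under the existing wording. State whether the timing phrase governs both halves of each criterion. Report how many patients this rule would add or remove compared with a rule without the date limit. If the number is zero, one sentence closes the point; if not, rerun the time-to-event analyses on the corrected cohort.

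The data are already abstracted, since sample collection dates are listed in Appendix 2. The costs are a few more patients with unknown status, an unknown row in the HER2 block of Table 15.1.10 (which now has only negative and discordant), matching protocol wording, and a small re-derivation of the cohort. Section 1 shows that this SAP version followed review of a manuscript draft, so the cohort has probably been assembled already. The count of affected patients should come first.

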2.1 Study Design

[figure not shown]
This is an observational, retrospective cohort study. Eligible patients will be identified from the Syapse Learning Health Network database and medical chart review will be conducted by Syapse Certified Tumor Registrars (CTRs). All study data are secondary data and will have been collected retrospectively from existing clinical data originally collected as part of routine care. This single-arm descriptive analysis will describe the patient characteristics, clinical attributes and treatment patterns of A/MBC patients with HR+/HER2- disease, who were treated with palbociclib + AI as first-line therapy. Additionally, clinical effectiveness outcomes for these patients will be evaluated between Feb 2015 and July 2019.

Study population

The study will include adult patients 18 years or older, diagnosed with HR+/HER2- A/MBC who initiated palbociclib combination therapy with AI as the first-line therapy on or after 03 February 2015 up to and including 31 July 2019. Patients for this study will be identified from the Syapse Learning Health Network database.

Preliminary analysis identified up to 1,074 patients with evidence of key primary inclusion criteria: breast cancer diagnosis and palbociclib treatment. Three to four hundred patients are expected to fulfil complete study inclusion criteria. Given the inclusion criterion requiring a qualifying treatment identification period between 03 February 2015 through 31 July 2019, and assuming a data cutoff date of 01 February 2020, the minimum follow-up available is therefore 6 months.

PFIZER CONFIDENTIAL

Data source

Patients will be identified and data will come from the Syapse Learning Health Network database which includes both inpatient and outpatient clinical and molecular data captured through manual abstraction and interoperative data feeds from a number of health system source systems, including:

- *Electronic medical record (EMR), including inpatient, outpatient oncology, ambulatory, surgical, etc.*
- *Electronic data warehouse (EDW)*
- *Laboratory information system (LIS)*
- *Picture archiving and communication system (PACS)*
- *Hospital based cancer registries*
- *Computerized physician order entry (CPOE)*

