7.2 Statistical Analyses

Objective1:

- a. To describe the demographic and clinical characteristics for patients diagnosed with HR+/HER2- A/MBC.

[figure not shown]
The numbers of breast cancer patients in the Syapse database meeting the eligibility criteria will be presented in an attrition table.

Demographic and clinical characteristics variables that will be reported include age, sex, race, insurance status, menopausal status, and region of residence at A/MBC diagnosis, stage of initial diagnosis, histology, Eastern Cooperative Oncology Group (ECOG) performance status (where ECOG score unavailable, Karnofsky performance status will be converted to corresponding ECOG score) and comorbid disease burden, HER2 and estrogen receptor (ER)/ progesterone receptor (PR) status, BRCA status, number and sites of distant metastasis at A/MBC diagnosis; modalities of treatment received prior to A/MBC diagnosis (chemotherapy, hormone therapy, surgery, radiation therapy), disease free interval (time between completion of adjuvant therapy and diagnosis of A/MBC) and follow-up time in the study. Descriptive analysis methods as detailed in Section 7.1 will be used for summarizing these parameters as appropriate.

- b. To describe the treatment patterns for patients diagnosed with HR+/HER2- A/MBC.

Treatment patterns generally include the record of all systemic anti-cancer therapies received from the index date through the end of the study period.

CCI

Description will include each of the following.

- Distribution of regimens, with the frequency and percentage of patients receiving each regimen within each line from the diagnosis of A/MBC through the end of the record.
- Description of sequence of regimens across lines, which shows how individual regimens were sequenced across lines through the end of the record of systemic therapy. Description will include the frequency and percentage of patients who received each specific sequence of treatments.
- Description of the dosing will include the starting dose, end dose, dose adjustment (dose increase and dose reduction), type of dose adjustment (dose modification, schedule changes, dose delay or hold), discontinuation reason (including death, progression, end of planned therapy, insurance changes, schedule change, dose delay, hold, cost, patient refusal, toxicity), and time to dose adjustment.

Objective2:

To examine clinical effectiveness for patients diagnosed with HR+/HER2- A/MBC.

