Kaplan-Meier survival analysis is used to descriptively characterize time to event outcomes. In this study, following time to event outcomes will be analyzed-

- Time to Real-world overall survival (rwOS)

[figure not shown]
The time origin for analysis of rwOS is start of the first-line therapy, and the terminal event is death. For patients not known to be deceased at the time of analysis, rwOS will be censored at the earliest of the last date of last contact or the end of the study period.

- Time to Real-world progression-free survival (rwPFS)

The time origin for analysis of rwPFS is start of the first-line therapy. Patients without a clinician-assessed progression event or death will be censored at the earliest of the following events: date of initiation of the 2nd line for patients with >1 line of therapy, date of last contact, or end of study period.

- Real world time to treatment discontinuation (rwTTD)

PFIZER CONFIDENTIAL

The time origin for analysis of rwTTD is start of the first-line therapy. Patients without first-line treatment discontinuation and who did not die will be censored at the earliest of the following events: last known usage of first-line treatment, or end of study period.

- Real world time to next treatment (rwTTNT)

The time origin for analysis of rwTTNT is start of the first-line therapy. Patients without a subsequent line of therapy initiation and who did not die will be censored at the earliest of the following events: date of last contact, or end of the study period.

- Real world time to chemotherapy (rwTTC)

The time origin for analysis of rwTTC is start of the first-line therapy. Patients who did not receive subsequent chemotherapy and who did not die will be censored at the latest of the following events: date of last contact, or end of the study period.

- Real world time to dose adjustment (rwTTDA)

The time origin for analysis of rwTTDA is start of the first-line therapy. Patients without a first-line treatment dose adjustment will be censored at the earliest of the following events: first-line treatment discontinuation, date of death, date of last contact, or end of the study period.

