Therapy start date	Year, month, day
Therapy end date	Year, month, day
Start reason	Recurrence; Progression; Other reason not related to worsening disease
Start reason source date	Year, month, day (can be linked to clinician confirmation date of recurrence/progression if start reason is recurrence/progression)
Stop reason	Categories including: Progression; Toxicity; End of planned therapy; Insurance changes; Treatment ongoing; Other
Stop reason source date	Year, month, day (can be linked to clinician confirmation date of recurrence/progression if stop reason is recurrence/progression)
Treatment part of clinical trial	Yes; No
Palbociclib-specific variables (captured in addition to above variables)	
Combination AI partner	Letrozole, Anastrozole, Exemestane
Concomitant LHRH Agonists	Goserelin (Zoladex), Histrelin (Vantas), Leuprolide (Eligard, Lupron), Triptorelin (Trelstar)
Dose 1 (start dose)	125mg, 100mg, 75mg
Dose 1 start date	Year, month, day
Dose n (where n>=2)	125mg, 100mg, 75mg
Dose n start date	Year, month, day
Dose n adjustment type or reason	Categories include schedule change; dose delay; hold; cost; patient refusal; toxicity

Variables that will be derived from curated data will include the following:

Data Elements	Description
-----------------------------	---------------------------

PFIZER CONFIDENTIAL

Age at A/MBC diagnosis	Age in years; age categories: <50, 50-64, 65 –74, ≥75 years (Exact list will depend on the expert de-ID approach)
Age at start of palbociclib treatment	Age in years; age categories: <50, 50-64, 65 –74, ≥75 years
Date of death	If patient vital status = deceased, date of death from the medical record (capturing from EMR, registries, third party integrations) (Availability of the exact date will depend on the Expert de-ID approach)
Palbo dose change ever	Yes; No
Disease Free Interval (DFI)	Months from the end of adjuvant therapy to the date of disease recurrence ≤12 months, 13-24 months, 25-36 months >36 months Unknown
Endocrine sensitivity	≥12 months without recurrence/progression after completion of endocrine therapy in the adjuvant setting

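### The trial-enrolment exclusion has no time anchor, so as naturally read it drops patients for events after index and tends to lengthen median rwPFS, rwTTNT and rwTTD

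*SAP*

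**What the plan says.** Exclusion criterion 1 in SAP Section 4 reads "Enrollment in an interventional clinical trial for A/MBC during the study observation period". The sentence introducing the exclusions states the consequence: "Patients meeting any of the following criteria will not be included in the study". The patient is therefore removed, not censored at enrolment.

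Eligible patients start palbociclib + AI as "first-line therapy after A/MBC diagnosis on or after 03 February 2015 through 31 July 2019". Time zero is that start; for example, "The time origin for analysis of rwPFS is start of the first-line therapy" (Section 7.2). Section 7.2 describes treatment patterns as the "record of all systemic anti-cancer therapies received from the index date through the end of the study period", and Section 2.1 adds that, "assuming a data cutoff date of 01 February 2020, the minimum follow-up available is therefore 6 months".

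Trial enrolment is not a censoring event for any endpoint. For rwPFS, patients without progression or death are censored at the earliest of "date of initiation of the 2nd line for patients with >1 line of therapy, date of last contact, or end of study period". Appendix 2 (Section 9.2) lists "Treatment part of clinical trial" as a yes/no element of the systemic therapy history.

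The other two exclusions look backward, one from the A/MBC diagnosis and one from the first palbociclib-containing line. Only criterion 1 has no such anchor.

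**The concern.** Whether a patient belongs to the cohort should be decidable at time zero. Under criterion 1 as naturally read, it can depend on something that happens years later.

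A patient who joins a trial after first line has by then stopped first-line treatment (an rwTTD event) and, if the trial supplies the next regimen or a later one, has started a new line (an rwTTNT event). Usually the patient has also progressed (an rwPFS event), though not always: a second line started without recorded progression is censored for rwPFS. Dropping such patients removes events selectively. Kaplan-Meier estimation cannot correct this, because the patients are absent from the risk sets altogether.

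These curves are primary outputs of a study whose purpose is description. The tables of later-line regimens and sequences lose the same patients.

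**Working it through.** **The plan's own figure.** From 31 July 2019 to 01 February 2020 is 185 days; 185 / 30.4375 = 6.08 months, which reproduces the stated 6-month minimum. From 03 February 2015 to 01 February 2020 is 1,824 days, so the longest follow-up is 1,824 / 30.4375 = 59.9 months. The index window is 1,639 days, or 53.8 months.

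**Assumptions not in the SAP.** Exponential rwPFS with median 20 months; uniform entry over the index window; a share p of progressors later joins a trial, immediately or after an exponential delay, and is removed if enrolment falls before cutoff.

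**Direction, by formula.** Let λ = ln 2 / 20 = 0.03466 per month, S(t) = exp(−λt), and G(t) the probability that follow-up exceeds t. With immediate enrolment, the hazard among retained patients is

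h*(t) = (1 − p) λ S(t)G(t) / [S(t)G(t) − p·P(t < T ≤ C)].

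Since P(t < T ≤ C) is less than S(t)G(t), h*(t) is below λ at every t. At t = 0:

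- P(T ≤ C) = 1 − [exp(−6.08λ) − exp(−59.93λ)] / (53.85λ) = 1 − (0.810 − 0.125) / 1.866 = 0.633.
- p = 0.05: h*/λ = 0.95 / (1 − 0.05 × 0.633) = 0.981.
- p = 0.20: h*/λ = 0.80 / (1 − 0.20 × 0.633) = 0.916.

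The ratio falls further as t increases.

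**Size, by simulation.** Median rwPFS in months after the exclusion, with an assumed truth of 20.0:

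| Progressors who enrol | Immediate | Mean delay 6 months | Mean delay 18 months |
|---|---|---|---|
| 1% | 20.1 | 20.1 | 20.1 |
| 3% | 20.3 | 20.3 | 20.2 |
| 5% | 20.5 | 20.5 | 20.4 |
| 10% | 21.0 | 21.0 | 20.8 |
| 20% | 22.4 | 22.2 | 21.7 |

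With immediate enrolment, 5%, 10% and 20% of progressors correspond to 3.2%, 6.3% and 12.7% of the cohort (p × 0.633). At 20%, the 24-month rate rises from 0.435 to 0.476.

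**Sensitivity to the assumptions.**

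- Loss to follow-up of 0.5% per month, 1-month mean delay, 20% enrolling: shift of about +2.5 months.
- True median of 24 months, 5-20% enrolling: about +0.5 to +3.3 months across delays from none to 18 months.
- Fast progressors enrol more often (twice the nominal rate before 10 months, half after; 0.5% monthly loss, 6-month mean delay): 20.8, 21.7 and 23.6 months at nominal rates of 5%, 10% and 20%.
- Only patients progressing after 10 months enrol (twice the nominal rate; same loss and delay): the median still rises, to 20.2, 20.4 and 21.1 months. At 20%, however, the 6-month rate falls from 0.811 to 0.790 and the 12-month rate from 0.659 to 0.637.
- Exclusion at baseline unrelated to outcome: the median stays at 20.0 months.

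rwTTNT and rwTTD were not simulated. Their direction rests on the same mechanism.

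**The case against.** **The period is undefined.** The criterion is marked as protocol text, and the protocol may define the observation period. That stands, so the point is put as a missing anchor with a natural reading. Nothing in the SAP supports a period ending at index. Even the calendar span of February 2015 to July 2019 named in Section 2.1 runs past index for nearly every patient. If a pre-index limit was meant, the wording still needs to say so.

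**The enrolment rate is assumed.** This also stands. The setting is US community oncology and nothing makes 5% a floor. At 1-3% the shift is small beside sampling error: with 350 patients, inside the expected 300 to 400, a 20-month median has a 95% sampling range of roughly 17 to 23.5 months. Unlike sampling error, though, this shift tends in one direction and is not reflected in the confidence interval.

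**The study is descriptive and attrition is reported.** No test or comparison is affected, and Table 15.1.1 will show the number excluded by criterion. That bounds the problem but does not show how many enrolled after index.

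**Changing the population now has a price.** Section 1 shows that this SAP version followed a manuscript draft, so redefining the primary population could be a results-aware change. This is a fair reason to prefer a sensitivity analysis.

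A reader might also infer that patients still on first line cannot be removed. The text does not support that: the criterion covers any interventional A/MBC trial, so someone enrolling during first line is removed too, possibly before any event.

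**Conclusion.** The concern holds in a limited form. As written, criterion 1 lets eligibility depend on post-index trial enrolment, and no other part of the SAP corrects this. The expected effect is longer median rwPFS, rwTTNT and rwTTD.

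For an assumed 20-month median rwPFS, the shift is about +0.1 to +0.3 months if 1-3% of progressors enrol, and about +0.4 to +2.4 months if 5-20% do. Those figures assume exponential times, uniform accrual, no loss to follow-up, enrolment unrelated to the timing of progression, and a delay from none to 18 months on average. They illustrate the possible size and do not estimate the bias in this cohort.

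A reader might infer that whole curves are pushed upward, or that overall survival is inflated. The documents support neither. Early landmarks can fall if mainly late progressors enrol, and the direction for rwOS is open. Excluding patients whose first-line treatment was itself given in a trial is a legitimate baseline restriction and is not at issue.

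**What to change.** 1. Limit exclusion 1 to patients who were in an interventional A/MBC trial at index, or whose first-line palbociclib + AI was trial treatment. The "Treatment part of clinical trial" element identifies the latter. Keep later enrolees for the first-line outcomes.
2. If the primary population is already fixed, leave it and add the analysis in point 1 as a sensitivity analysis, specified in a dated amendment before it is run.
3. For patients who enrol before a first-line event, and for rwOS and rwTTC, add a sensitivity analysis censoring at enrolment. State that this censoring may be informative.
4. Split the exclusion 1 count in Table 15.1.1 into enrolment at or before index, during first line, and after first line.

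**Cost.** Wording changes, one added analysis set and one expanded table row. Trial regimens would appear in the later-line tables and should be flagged. Some rwOS time would be spent on trial therapy. The SAP does not say whether excluded patients were fully abstracted, so some records may need abstraction. If that is not feasible, the count by timing and a statement of the likely direction are the minimum.
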